**Table 1. Handling of Intercurrent Events for the Primary Estimand**

Intercurrent event	Data collection and analysis
Treatment discontinuation	Events occurring up until the EoT date will be included in the analysis. Patients without event will be censored at the EoT date.
Study discontinuation	Events occurring up until the EoT date will be included in the analysis. Patients without event will be censored at the EoT date.
Concomitant anticoagulation therapy	Patients who use concomitant anticoagulation and continue on study will be analyzed by the treatment policy strategy, i.e., no adjustment will be made. Patients who use concomitant anticoagulation without a primary event before the EoT date will be censored at the EoT date.
Death	Patients who experienced primary event before death will be included in the analysis. Patients who did not experience any bleeding event before death will be censored at the time of death reflecting a while alive strategy.

#### 4.1.5. Population-level Summary for Comparison between Treatment Conditions

The treatment effect will be quantified by the hazard ratio comparing the hazard rate for abelacimab to the hazard rate for rivaroxaban in first occurrence of composite of ISTH-defined major bleeding or CRNM bleeding events. The basis for comparison will be the Cox proportional hazards model including treatment and the following two stratification factors as covariates: planned use of concomitant antiplatelet medication use (e.g. aspirin and/or P2Y12 inhibitor) for the duration of the trial; CrCl (Cockcroft-Gault)  $\leq 50$  ml/min.

#### 4.2. Estimands for the secondary objectives

The estimands attributes for all secondary endpoints are defined in the same manner as for the primary endpoint described above.

## 5. Data Handling

### 5.1. Time Points and Visit Windows

#### 5.1.1. General Definitions

All assessment days will be related to the first day of first dose of treatment.

Day 1 is defined as first dose of treatment. Relative days after Day 1 are calculated as (assessment date – Day 1 date) + 1. Relative days prior to Day 1 are calculated as (assessment date – Day 1 date). The day prior to Day 1 is Day -1. Day 0 is not defined.

The date of the first dose of treatment for each patient will be taken from the electronic case report/record form (eCRF) page. If the date in this eCRF page is missing, alternatively the date of randomization will be used.

The date of the last dose of treatment for each patient will be taken from the eCRF page. For subjects receiving abelacimab, the last dose is latest Date of injection from the Study Drug SC Administration eCRF page.

For subjects receiving rivaroxaban, the last dose will come from the following sources, depending on the patient status:

- For those who permanently discontinue treatment, the last dose will be the permanent discontinuation date.
- For those who died but did not permanently discontinue treatment before death, the last dose will be the death date.
- For all other subjects who completed the treatment per the EoT visit page, the last dose will be the EoT visit date.
- If the last dose date is still missing, the last dose will be the last date pills were returned from the Study Drug PO Accountability page.

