#### **6.5 Study treatment interruptions**

Study drug may be interrupted at the Investigator's discretion for medical or surgical reasons.

Reasons for temporary study drug interruption may include a planned invasive procedure or surgery for which one would typically stop oral anticoagulation (see [Section 6.5.2](#)); clinical indication for a prohibited medication (see [Section 6.7.1](#)); a bleeding AE (see [Section 8.2](#)); or any other medical condition where the Investigator judges that it is in the best interests of the patient to temporarily interrupt study drug.

Since patients with AF are at underlying risk of stroke and systemic embolism, the duration of any study drug interruption should be kept to the minimum possible unless there is a contraindication to anticoagulation. Patients who have interrupted study drug should be re-evaluated regularly by the Investigator to determine the risks and benefits of resuming study drug.

For patients assigned to rivaroxaban, the eCRF page for study drug interruption should be completed for any temporary study treatment interruptions of 2 or more consecutive days and include the date/time of the last dose, the reason for the temporary interruption (e.g., procedures), and other required details.

For patients assigned to abelacimab, the eCRF for study drug interruption is required for any missed study treatment >45 days from the previous dose and include the date/time of the last dose, the reason for the temporary interruption (e.g., procedures), and other required details.

There is no limit on either the number of study drug temporary interruptions or the maximum length of a study drug temporary interruption. As long as the study has not completed, a patient who has interrupted study drug can resume study drug as soon as it is determined to be appropriate by the Investigator.

A patient who continues to be on study treatment interruption when the randomized period of the study has completed will be considered to have permanently discontinued study drug, will not be eligible for the extension and should complete a PSDD visit and a EoS visit approximately 30 days later (see [Section 6.6](#)).

Investigators are strongly encouraged to call the [REDACTED]

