#### 6.6 Permanent study drug discontinuation

Permanent study drug discontinuation (PSDD) is allowed at the Investigator's discretion or patient's request at any time. The Investigator should call the [REDACTED] in case of potential PSDDs.

If a patient has what is expected to be a permanent discontinuation of study drug, the patient should complete PSDD visit procedures outlined in the Assessment Schedule ([Appendix 3](#)). At the PSDD visit, unless the patient has a contraindication to anticoagulation, Investigators should arrange patients to be transitioned to appropriate SoC anticoagulation therapy minimizing any gap in anticoagulation since patients with AF are at underlying risk of stroke and systemic embolism (see [Section 7.1](#)).

Patients who permanently discontinue study drug will have an EoS visit approximately 30 days after the PSDD visit and then will be contacted periodically, approximately every 12 weeks, by telephone for SAEs and endpoints (see [Section 7.2](#)) until the site has been notified by the SSC that the randomized period of the trial has ended at which point the patient's participation in the study can be considered completed. Sites should not enter the patient as "complete" in the eCRF until the study has been declared complete, unless the patient has withdrawn their consent to be followed by all possible methods (i.e., in person, remotely, via third party) and refuses to permit review of the medical records.

In certain situations, patients who have previously permanently discontinued study drug and had an PSDD Visit can be allowed to resume study drug. The Investigator should contact the [REDACTED] to determine whether or not a patient who completed a PSDD visit can resume

study drug.

Any patient who permanently discontinues study drug and also wishes to withdraw consent for participation in the study must complete the protocol-specific withdrawal of consent procedures (see [Section 7.3](#)). The Investigator should contact the [REDACTED] to discuss cases in which a patient wishes to withdraw before the decision is made and withdrawal procedures are begun. Withdrawal procedures can begin only after discussion and confirmation that the patient's desire to withdraw full consent.

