### 2.2.3. Exploratory Objectives

### 2.3. Sample Size and Power

The primary endpoint is the composite of major or CNRM bleeding. The study is event driven. At the start of trial it was assumed a HR of 0.60 for each dose of abelacimab compared with rivaroxaban, thereby, a total of at least 166 events would provide at least 80% power for each abelacimab arm vs. rivaroxaban with a 2-sided alpha of 0.05. Given an expected 15% per year event rate in the rivaroxaban arm, a 10% annual dropout rate (death, withdrawal of consent,

lost-to-follow-up), approximately 1,200 patients would provide the requisite number of events over an approximate total trial duration of 27 months.

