### 2.1. Change in the EoT date and EoS date in the randomized phase of the study for patients enrolled in the extension in section 3.1 of the SAP

The analysis dates to be used are defined as:

- EoT date = Earliest of a) the last dose+60 days or b) the EoT visit **-1 day** or c) death date or d) withdraw consent date or e) EoS visit date
- EoS date = Earliest of a) EoS visit or b) death date or c) withdraw consent date or d) lost to follow-up date; if no EoS date available, then impute EoT visit date **-1 day**

**As per the protocol version 5.0, EoT visit and Extension Day 1 will occur on same day.** In the event that there is an open-label extension period in which the patient enrolls, the following analysis dates to be used are defined as:

- EoT date = **Earlier of a) the last dose+60 days or b) the EoT visit -1 day**
- EoS date = **the EoT visit -1 day**
- EoE date = Earliest of a) the last dose+60 days or b) the EoE visit or c) death date
- EoS extension date = EoS visit; if no EOS visit date available, then impute EoE date

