### 2.2. Change in the last dose dates in section 5.1.1 of the SAP

The date of the last dose of treatment for each patient will be taken from the eCRF page. For subjects receiving abelacimab, the last dose is latest Date of injection from the Study Drug SC Administration eCRF page (**before the extension day 1 for patients who enroll in the extension**).

For subjects receiving rivaroxaban, the last dose will come from the following sources, depending on the patient status:

- For those who permanently discontinue treatment, the last dose will be the permanent discontinuation date.
- For those who died but did not permanently discontinue treatment before death, the last dose will be the death date.
- For all other subjects who completed the treatment per the EoT visit page, the last dose will be the EoT visit date **-1 day**.
- If the last dose date is still missing, the last dose will be the last date pills were returned from the Study Drug PO Accountability page.

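### The primary on-treatment window counts from the last injection for abelacimab but from the discontinuation or death date for rivaroxaban, so interruptions that are never resumed are treated unequally across arms

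*SAP*

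**What the plan says.** SAP 3.1, as revised in Addendum 2.1, ends on-treatment follow-up at the earliest of several dates. These are last dose + 60 days, the EoT visit (minus one day in the addendum), death, withdrawal of consent and, last in the list, "e) EoS visit date". SAP 6.6.1 censors the primary endpoint at this date. Protocol 10.1 states a single rule for all arms: on treatment if within 60 days of the last dose, up to the EoT visit.

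The source of the last dose differs by arm:

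- **Abelacimab** (SAP 5.1.1, Addendum 2.2): "the last dose is latest Date of injection from the Study Drug SC Administration eCRF page".
- **Rivaroxaban** (same sections): "For those who permanently discontinue treatment, the last dose will be the permanent discontinuation date". For patients who die without a recorded discontinuation it is the death date.

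Addendum 2.2 moved the rivaroxaban date for treatment completers by one day but left these two rules alone. SAP 6.7.1 uses a further rivaroxaban end date, the last drug return, for exposure.

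On interruptions, Protocol 6.5 says: "There is no limit on either the number of study drug temporary interruptions or the maximum length of a study drug temporary interruption". A patient still interrupted "when the randomized period of the study has completed will be considered to have permanently discontinued study drug", and then has a PSDD visit and an EoS visit about 30 days later. For rivaroxaban interruptions of two or more consecutive days, the same section requires the eCRF to record the date and time of the last dose. Protocol 6.6 says that a patient who stops permanently "will have an EoS visit approximately 30 days after the PSDD visit".

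**The concern.** The same 60 days are counted from an observed drug-taking event in two arms and from a status date in the third. For most patients the two probably lie close together. They can lie far apart when a rivaroxaban patient interrupts and never restarts. If the interruption is still open at study end, discontinuation is recognised only then, and the EoS visit cap gives no protection because that visit follows the late PSDD visit. If the patient dies during the interruption with no discontinuation recorded, follow-up runs to death.

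At stake is the primary comparison. Extra time off study drug, and any bleeding in it, enters the rivaroxaban arm under a rule that would exclude it from the abelacimab arms. None of the sensitivity analyses in SAP 6.6.2 replaces the rivaroxaban last-dose date, so the report would not show whether this matters.

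**Working it through.** **1. The plan's own figure.** Inputs from SAP 2.3: HR 0.60, "at least 80% power for each abelacimab arm vs. rivaroxaban", "with a 2-sided alpha of 0.05", 166 events in total. Allocation is 1:1:1 (Protocol 6.2). The Protocol's sample size text prints 0.69 where its synopsis and SAP 2.3 print 0.60; only 0.60 fits 166 events.

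- Pairwise events (Schoenfeld): 4 × (1.960 + 0.842)² / (ln 0.60)² = 120.3.
- Three arms with hazards 1 : 0.6 : 0.6: 120.3 × 2.2/1.6 = 165.4, rounded up to 166. Reproduced.
- Pairwise events within 166: 166 × 1.6/2.2 = 120.7.
- Power: Φ(0.511 × √120.7 / 2 − 1.96) = 80.1%.

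**2. Days added by the rivaroxaban rule, by type of patient.**

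- *Discontinuer.* Let g be the days from last tablet to the PSDD visit, and suppose that visit supplies the discontinuation date. The EoS visit falls at g + 30. The window now ends min(g + 60, g + 30) = g + 30 days after the last tablet. Counted from the last tablet it would end at min(60, g + 30). The difference is max(0, g − 30): 0 days for g = 14 or 30, 30 for g = 60, 150 for g = 180. If the discontinuation date is the day the patient stopped, nothing is added.
- *Death during an interruption, no discontinuation recorded.* EoT is capped at death, so the rule adds max(0, gap − 60): 0 days for a 60-day gap, 30 for 90, 120 for 180.
- *Interruption still open at study end.* Illustration: last tablet at month 6, PSDD visit at month 21. Then g = 15 × 30.44 = 457 days, and the rule adds 457 − 30 = 427 days. An abelacimab patient with the same history is censored 60 days after the last injection.

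**3. Effect on the hazard ratio.** All inputs here are assumptions. A share p of rivaroxaban patients never resume. Their last tablet is uniform over T = 1.75 years of follow-up. Off-drug hazard is r times on-drug hazard. The HR is 0.60 when the last tablet is used.

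- Mean time on drug in this group: 0.875 years. Mean time off drug: 0.875 years.
- Part of the off-drug time inside the 60-day tail, with w = 60/365.25 = 0.164: w − w²/(2T) = 0.157 years.
- Relative rivaroxaban rate under the SAP rule: 1 − 0.5p(1 − r).
- Relative rate with the last tablet: [1 − p + p(0.875 + 0.157r)/1.75] / [1 − p + p(0.875 + 0.157)/1.75].
- Observed HR = 0.60 × (last-tablet rate) / (SAP rate). Power = Φ(|ln HR| × √120.7 / 2 − 1.96).

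Example, p = 15%, r = 0: SAP rate 0.925, last-tablet rate 0.986, HR = 0.60 × 0.986/0.925 = 0.639, power 69%.

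| p | r = 0 | r = 0.5 | r = 1 | r = 1.3 |
|---|---|---|---|---|
| 3% | 0.607 (78%) | 0.604 (79%) | 0.600 (80%) | 0.598 (81%) |
| 5% | 0.613 (77%) | 0.606 (79%) | 0.600 (80%) | 0.596 (81%) |
| 10% | 0.626 (73%) | 0.613 (77%) | 0.600 (80%) | 0.593 (82%) |
| 15% | 0.639 (69%) | 0.619 (75%) | 0.600 (80%) | 0.589 (83%) |

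The documents give neither p nor r. For follow-up, Protocol 1.2.2 says only that mean time on treatment exceeded 12 months in September 2022.

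**The case against.** A reader might infer that the rivaroxaban date is purely administrative, that off-drug time enters the rivaroxaban arm only, and that its bleeding rate is therefore diluted. The documents do not support that much.

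- **The date may be the stopping date.** The Protocol glossary and section 7.2 define discontinuation by when drug is permanently stopped. For ordinary discontinuers the recorded date may be at or near the last tablet. Even if it is the PSDD visit, an on-schedule EoS visit removes the effect for gaps up to 30 days. This stands, and confines the problem to long interruptions that are never resumed. Protocol 6.5 does not say outright that such patients receive a study-end discontinuation date, but they are reclassified and given their PSDD visit then, and nothing in the SAP redirects the date to the last tablet.
- **Off-drug time is not confined to one arm.** Every arm has a tail after the last dose, and interruptions that are later resumed are uncensored in every arm. This stands.
- **Lower bleeding off drug is not given.** Discontinuers are to move to standard-of-care anticoagulation (Protocol 6.6), interruptions may be due to a bleed or to the need for another anticoagulant (6.5, 6.7.1), and the primary estimand makes no adjustment for other anticoagulants. Sensitivity analysis 3 censors for them. An off-drug hazard equal to or above the on-drug hazard is plausible, so dilution is one possible outcome among several.
- **The group may be small.** Protocol 6.5 asks for interruptions to be minimised and re-evaluated, and 6.6 for a PSDD visit once stopping is expected to be permanent. At 3-5% never resuming, HR moves by at most 0.013. Any move toward 1 works against abelacimab and cannot create a false bleeding benefit.

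These points limit the size and remove any certain direction. They do not make the rule the same in each arm.

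**Conclusion.** The concern holds for a defined subgroup: rivaroxaban patients whose interruption is still open at study end, or began more than 60 days before death with no discontinuation recorded. For them the SAP can extend on-treatment follow-up well past last tablet + 60 days, while an abelacimab patient with the same history is censored. That departs from the common rule in Protocol 10.1.

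Under the assumptions in the table, the HR could lie anywhere from about 0.589 to 0.639 against a planned 0.60, and power from about 83% down to 69%, with no change when off-drug and on-drug hazards are equal. This is a modest flaw in the primary analysis that should be corrected. It is not evidence that the result is biased in a known direction.

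The EoS visit cap is a separate matter. It is tempting to delete it so that the tail is 60 days for everyone. For a rivaroxaban patient with a prompt PSDD visit that would lengthen the tail from about 30 to 60 days. If 20% discontinue, this adds 0.20 × 30 / (1.75 × 365.25), about 1% of rivaroxaban person-time, all of it off study drug.

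**What to change.** Amend the rule in SAP 5.1.1 and Addendum 2.2. Define the rivaroxaban last dose as the last tablet taken wherever the interruption eCRF records it, including for patients who die during an interruption or are still interrupted at study end. Otherwise use the discontinuation date, and state what that date represents. Leave the EoS visit cap in place.

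The database was locked on 08Mar2024, so record the change in a dated addendum and report the primary Cox analysis with this date at least as a sensitivity analysis. State how many rivaroxaban patients are affected and how much person-time and how many events move.

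The cost is one derived date to reprogram, one extra analysis, and a post-lock change to disclose. For interruptions, the Protocol already requires the last-dose date to be collected. Neither document says that a discontinuation form records it, which is why the fallback is needed.

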#### 5.1.2. Screening / Baseline Period

For all patients, the screening period is defined as the period from informed consent to randomization. For some variables, data from more than one assessment within the screening Period can be collected prior to randomization.

The baseline value for a variable is therefore defined as the last non-missing value collected before randomization.

Assessments carried out on day of randomization are considered to have taken place before randomization if the corresponding times have not been recorded.

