**Table 3-1 Transition Guidelines**

Baseline anticoagulant therapy	Instructions
Direct oral anticoagulant (DOAC)	The patient's last dose of DOAC should be approximately 12-24 hours prior to receiving study medication on Day 1.
Vitamin K antagonist (VKA)	After enrolled and found to be eligible, patients should have their VKA discontinued, and INRs should then be performed every 1 to 2 days based on initial INR. The patient should be randomized as soon as possible (ideally within 36 hours) once the INR is <2.5. Sites may collect repeat INR samples using point of care devices or send for local analysis, in which case results will remain as part of source documentation only.

Eligible patients will be randomized into one of the following treatment groups:

- Treatment group 1: abelacimab 90 mg s.c. monthly
- Treatment group 2: abelacimab 150 mg s.c. monthly
- Treatment group 3: rivaroxaban 20 mg p.o. once per day with the evening meal  
[Note: Patients with a CrCl  $\leq$ 50 ml/min by the Cockcroft-Gault equation will receive the 15 mg p.o. daily dose of rivaroxaban]

Patients will be randomized on Day 1, which will be the date of the first administration of study drug. Patients will be contacted by phone on Day 8 for a general health and safety check. Patients will be assessed for AEs and changes in concomitant medication every month during the study treatment period; patients assigned to abelacimab will receive their s.c. injection and patients assigned to rivaroxaban will have study medication compliance assessed during these monthly visits. Every third month, these visits will include additional safety assessments and collection of blood samples for laboratory analysis.

Where permitted, visits as indicated in the Assessment Schedule (Appendix 3), may be conducted at home by staff qualified to administer s.c. injections or by telephone/video-call, depending on treatment arm. In the case of visits conducted in the patient's home, with the patient's consent, the Investigator and/or delegated staff will arrange for the service and will provide the patient's name and address to the personnel conducting the in-home visit, which will be either site staff or locally contracted agency staff.

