### 4.2 Exclusion criteria

Patients fulfilling any of the following criteria are not eligible for inclusion in this study:

1. Use of other investigational drugs within 5 half-lives prior to enrollment or until the expected pharmacodynamic effect has returned to baseline, whichever is longer
2. History of hypersensitivity to any of the study drugs (including rivaroxaban) or its excipients, to drugs of similar chemical classes, or any contraindication listed in the label for rivaroxaban (See [Section 6.7.1](#) for examples)
3. Patients with an intracranial or intraocular bleed within the 3 months prior to screening
4. Clinically significant mitral stenosis (valve area  $<1.5$  cm^2)
5. Mechanical heart valve or other indication for anticoagulation therapy other than atrial fibrillation (e.g., venous thromboembolism)
6. Known presence of an atrial myxoma or left ventricular thrombus
7. History of left atrial appendage closure or removal
8. Active endocarditis
9. Systolic BP  $>180$  mm Hg or diastolic BP  $>100$  mm Hg on repeated measurements at screening
10. Planned invasive procedure with potential for uncontrolled bleeding (e.g., major surgery)
11. Any stroke within 14 days before randomization or TIA within 3 days before randomization
12. A CrCl  $<15$  mL/min or on dialysis at the time of Screening
13. Platelet count  $\leq 70,000/\text{mm}^3$  at the Screening Visit
14. Hemoglobin  $<8$  g/dL at the Screening Visit
15. aPTT or PT  $>1.5$  times the upper limit of normal (ULN) at the Screening Visit, if the patient is not on an anticoagulant
16. Women of child-bearing potential (WOCBP), defined as all women physiologically capable of becoming pregnant, unless they agree to use highly effective methods of contraception during their participation in the trial and for at least 10 weeks after the last dose of abelacimab for women randomized to abelacimab. Highly effective contraception methods include:
  - Total abstinence (when this is in line with the preferred and usual lifestyle of the patient). Periodic abstinence (e.g., calendar, ovulation, symptothermal, post-ovulation methods) and withdrawal are not acceptable methods of contraception

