### 10.6.1 Pharmacodynamics

All pharmacodynamic endpoints will be summarized by visit and treatment group including the ratio to baseline for each treatment along with their associated confidence intervals.

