Absolute change (unit) = (post-baseline value – baseline value).

All laboratory data will be reported in SI units. All quantitative laboratory test values at each assessed visit will be compared with the relevant reference range in SI units and categorized as:

- Low: Below the lower limit of the reference range.
- Normal: Within the reference range (upper and lower limits included).
- High: Above the upper limit of the reference range.

For analysis purposes, values preceded by a “<” (i.e. those below the limits of quantification) will be considered as half of the value between the lower limit of quantification and 0; values preceded by a “>” sign (i.e. those below or above the limits of quantification) will be considered equal to the upper limit of quantification.

Laboratory data will be summarized by default descriptive summary statistics for continuous and categorical variables for the On-Treatment Analysis Set by treatment group and overall as follows:

- Observed values and change from baseline at each assessed visit for each standard continuous laboratory parameter;
- Number and percentage of patients with categorized (low, normal and high) values at each visit for hematology and serum chemistry;
- Number and percentage of patients with categorized (low, normal and high) values shift relative to the reference range at baseline compared to each post-baseline visit for the following laboratory evaluations: hemoglobin, hematocrit, total bilirubin,

alkaline phosphatase, aspartate aminotransferase (AST), alanine aminotransferase (ALT), and creatinine;

Listings of all clinical laboratory data including derived change from baseline will be provided for the On-Treatment Analysis Set. Within each listing, laboratory values outside the normal ranges will be flagged as either high or low. Box plots of laboratory parameters over time will be presented.

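### In patients switching from an anticoagulant, the aPTT and PT/INR baseline may be taken under residual DOAC or VKA effect, so the planned change and ratio to baseline mix washout with study-drug effect

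*SAP*

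**What the plan says.** SAP 5.1.2 defines baseline for every variable and every patient: "The baseline value for a variable is therefore defined as the last non-missing value collected before randomization". It adds: "Assessments carried out on day of randomization are considered to have taken place before randomization if the corresponding times have not been recorded".

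Protocol Table 3-1 governs patients who arrive on oral anticoagulation. For DOACs: "The patient's last dose of DOAC should be approximately 12-24 hours prior to receiving study medication on Day 1". For VKAs: "The patient should be randomized as soon as possible (ideally within 36 hours) once the INR is <2.5". Patients not on oral anticoagulation at screening are also eligible (Protocol 3.1.2). The documents do not give the share of each group.

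The assessment schedule (Protocol Table 16-1) places pre-treatment PT/INR and aPTT at Screening and Day 1 only. The repeat INRs used to time randomization may stay in source documents.

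Two planned outputs use the baseline. Protocol 10.6.1 summarizes pharmacodynamic endpoints, which include aPTT, "including the ratio to baseline for each treatment along with their associated confidence intervals". SAP 6.7.4 plans "Observed values and change from baseline at each assessed visit for each standard continuous laboratory parameter"; its Table 2 lists aPTT and PT/INR, and it derives change from the 5.1.2 baseline. SAP 6.8.1 mentions only summaries by visit and group, and leaves further PK/PD detail to a separate SAP.

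SAP 6.4.2 summarizes current anticoagulant use and the agent at baseline. No aPTT or INR analysis in the available text is split by it.

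**The concern.** A within-arm change or ratio can be read as a drug effect only if its reference value is free of other drugs acting on the same test. For a switcher the plan does not require such a value. The Day 1 sample falls within a day or so of a DOAC dose, or at any INR under the VKA threshold. A Screening sample is no safer, because the VKA is stopped only after eligibility is established.

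The protocol itself recognizes that anticoagulants affect these tests. Exclusion 15 applies its aPTT/PT limit "at the Screening Visit, if the patient is not on an anticoagulant", so that limit does not constrain switchers' baselines either.

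At stake is how the coagulation tables are read. An INR fall in an abelacimab arm could be taken as a drug finding when it is VKA washout. An aPTT ratio pooled over switchers and non-switchers could sit below the true prolongation.

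**Working it through.** The plan states no baseline aPTT or INR, no switching share and no expected change, so there is no figure to reproduce. The check is whether the rules allow a contaminated baseline, which way the error runs, and how large it would be under stated assumptions.

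**Do the rules allow it?** Yes. SAP 5.1.2 takes the last pre-randomization value. Table 3-1 permits that value 12-24 hours after a DOAC dose or at INR below 2.5, and no drug-free sample is scheduled. One further gap: if the Day 1 draw is timed after randomization but before dosing, SAP 5.1.2 sends the baseline back to Screening, where the INR threshold does not apply. SAP 5.1.3 would assign the same draw to the baseline period.

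**INR, VKA switchers in the abelacimab arms**

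Change per patient = on-treatment INR − baseline INR. The baseline limit (<2.5) is from Table 3-1. The on-treatment value of 1.0 is assumed.

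- Baseline 2.49: 1.0 − 2.49 = −1.49, or about −1.5
- Baseline 2.0: 1.0 − 2.0 = −1.0
- Baseline 1.5: 1.0 − 1.5 = −0.5

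Arm mean = s × (1.0 − b), where s is the assumed share switching from VKA, b their baseline INR, and all other patients are taken to have no change.

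- s = 0.10, b = 1.5: −0.05
- s = 0.10, b = 2.5: −0.15
- s = 0.50, b = 1.5: −0.25
- s = 0.50, b = 2.5: −0.75

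**aPTT, abelacimab arms**

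Let R be the true ratio (2.0, assumed), k the factor by which residual drug inflates baseline, and p the share switching. Neither k nor p is in the documents. Pooled geometric mean ratio = R / k^p:

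| k | p = 0.5 | p = 0.7 | p = 1 (switchers only) |
|---|---|---|---|
| 1.0 | 2.00 | 2.00 | 2.00 |
| 1.1 | 1.91 | 1.87 | 1.82 |
| 1.25 | 1.79 | 1.71 | 1.60 |
| 1.5 | 1.63 | 1.51 | 1.33 |

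The absolute change, in units of the drug-free baseline, is R − (p·k + 1 − p). With R = 2.0 the shortfall is p(k − 1). At p = 0.5 that is 5% of the true change for k = 1.1 and 25% for k = 1.5.

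**Does it reach between-arm contrasts?** If randomization gives both dose arms the same k and p, then (R150/k^p) / (R90/k^p) = R150/R90. The common factor cancels, so the distortion is in the within-arm reading.

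**The case against.** The case for leaving the plan alone has real force.

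- The last pre-randomization value is a conventional baseline, and observed values by visit are already planned next to the changes. This stands: the observed values are unaffected.
- Randomization should balance prior therapy across arms. This stands for between-arm contrasts, including 150 mg against 90 mg. It does not rescue a within-arm change or ratio, which is what is tabulated.
- The ratio to baseline appears only in the protocol, and SAP 6.8.1 defers PK/PD detail to a separate plan that may already contain the split. This is possible for the ratio. It does not cover the SAP 6.7.4 change tables, and SAP Section 7 declares no departure from the protocol's planned analyses.
- No passage says that aPTT is raised 12-24 hours after a DOAC dose or at INR below 2.5. Exclusion 15 concerns Screening, when a patient may be fully treated. This stands, which is why the aPTT range starts at no effect.

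A reader might infer that abelacimab's aPTT effect is shown to be understated throughout the trial. The documents do not support that: patients not on an anticoagulant are unaffected, the switching share is not given, and the residual effect has no stated size. A reader might also infer that the ratio is meant to be set against the more than 2-fold Phase 1 prolongation in Protocol 1.2.2. That result is background in healthy subjects. No such comparison is planned, and the dose rationale rests on FXI inhibition.

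**Conclusion.** The point holds for patients switching from an anticoagulant, and only for outputs that use their aPTT or PT/INR baseline.

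The INR part is the firmer. The rules admit VKA patients at any INR below 2.5, so their INR on abelacimab will appear to fall. The 1.5 fall is an upper case under the Day 1 threshold, not a typical value. The arm-mean range depends on the assumed VKA share, baseline INR and on-treatment INR. It is stated for the abelacimab arms only, because rivaroxaban patients move to another oral anticoagulant.

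The aPTT part is certain only in direction: any inflation lowers the ratio. Its size is unknown and may be nil.

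Severity is minor. The primary and secondary analyses use adjudicated bleeding and do not draw on these values. No test, dose decision or stopping rule in the available text depends on the aPTT ratio or INR change.

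**What to change.** Present the aPTT and PT/INR change and ratio to baseline by baseline anticoagulant use (none, DOAC, VKA), using the items already summarized under SAP 6.4.2. Keep the planned observed values alongside. Read the baseline-referenced drug effect from patients not on an anticoagulant at baseline. Footnote switchers' changes as confounded by withdrawal of the prior drug. State which Day 1 draw counts as baseline when it falls between randomization and first dose, so that SAP 5.1.2 and 5.1.3 agree. If the separate PK/PD plan already has the split, cross-refer to it and apply the same split to the SAP 6.7.4 tables.

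The transition rules need no change for this purpose, and no new data are needed. The cost is a few extra by-visit tables and lower precision in the unexposed stratum, whose size the documents do not give. The SAP addendum records final database lock on 08Mar2024, so the split should be labelled as added after lock.
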